The purpose of this SAP is to outline the planned analyses to be completed for the "ChAllenging to Food with Escalating ThrEsholds for Reducing Food Allergy" (CAFETERIA) trial (protocol number AADCRC-ISMMS-03). The SAP is based on protocol [clinicaltrials.gov ID NCT03907397] revision 3.0 finalized November 2021. This SAP covers study endpoints related to the primary and secondary clinical objectives and does not address the primary and secondary mechanistic objectives. The analyses identified in this SAP will be included in abstracts and manuscripts reporting the results of the trial. Exploratory analyses not necessarily identified in this SAP may also be performed. Any post hoc, or unplanned, analyses not explicitly identified in this SAP will be clearly identified as such in any published papers from this study. This SAP may be updated in response to additional developments, either within or outside the trial. All revisions will be made prior to the data lock and the primary analysis.

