The primary mechanistic objectives are to elucidate immune mechanisms induced by daily ingestion of sub-threshold amounts of peanut, and to identify biomarkers of and functional pathways underlying desensitization potential. We will test if peanut ingestion is associated with the following immune and transcriptomic processes:

- Suppression of serum peanut-specific IgE
- Increase in serum peanut-specific IgG and IgG4
- Change in peanut IgE and IgG4 epitope binding scores
- Decrease in basophil activation tests
- Decrease in peanut-specific multifunctional Th2 cells
- Increase in peanut-specific regulatory T cells
- Change in peripheral blood transcriptional signatures
- Up and downregulation of distinct gene ontology pathways

Primary Mechanistic Endpoints

- 1. Change in peanut and Ara h 2-specific IgE from baseline as measured by ImmunoCAP assay
- 2. Change in peanut and Ara h 2-specific IgG4 from baseline as measured by ImmunoCAP assay
- 3. Change in peanut epitope-specific IgE and IgG4 binding score from baseline
- 4. Change in basophil activation from baseline, as measured by %CD63+ basophil by flow cytometry/mass cytometry
- 5. Change in frequency of peanut-specific Th2 cells, as measured by CD154 and cytokine co-expression after in vitro stimulation with peanut
- 6. Change in frequency of peanut-specific T cells expressing CD137 and regulatory markers or producing IL-10 after in vitro stimulation with peanut
- 7. Change in peripheral blood transcriptional signature via RNAseq

Secondary mechanistic objectives

Secondary mechanistic objectives are to:

- Determine if immune and transcriptomic measures obtained early in the course of ingestion exposure can predict the development of desensitization or sustained unresponsiveness
- Identify immune and genomic biomarkers of the high threshold phenotype
- (Exploratory) Identify early-appearing functional pathways underlying a successful desensitization course

Secondary Mechanistic Endpoints

- 1. Immune and transcriptomic measures obtained early in the course of ingestion exposure that predict the development of desensitization or sustained unresponsiveness
- 2. Immune and genomic biomarkers of the high threshold phenotype
- **3**. (**Exploratory**) Early-appearing functional pathways underlying a successful desensitization course.

Statistical Analyses

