Immunocap Assay: Changes in serum component proteins measured through ImmunoCAP assay will be compared between randomization groups using linear mixed effects models for data collected at baseline, week 16 and the desensitization double-blind, placebo-controlled food challenge visit. The analysis will include a random subject effect and the fixed effect of randomization assignment, time, interaction between randomization assignment and time, and age. Spline models may be considered if the curves exhibit non-linear trends. Values below the limit of detection (LOD) will be imputed as X/sqrt(x)). The linear mixed effects model has the advantage that the estimation of the model parameters will be unbiased even in the presence of missing outcomes, assuming that the missing values depend only on the observed values (missing at random). If the missing at random assumption is not plausible, pattern-mixture modeling (which stratifies subjects by their pattern of missing data) will be used.

Cell population frequency: Quantile-linear mixed effects models will be used for the frequency of %CD63+ basophil, peanut-specific Th2 cells and T cells.

BBEA Assay: The bead-based epitope assay (BBEA) protocol will be used to obtain peanut specific of 64 15-mer epitopes derived from key peanut allergens—34 from Ara h 1, 16 from Ara h 2, and 14 from Ara h. All data processing, quality control, and analyses will be performed in R (version 4.3.3; R Foundation, Vienna, Austria). Binding scores for each epitope in the IgE and IgG4 assays will be obtained via *bbeaR*. Plate effect will be assessed using Principal Variation Component Analysis along with age strata, randomization assignment, visit, the interaction between randomization assignment and visit, and participant. If Plate effect is considered to be large, ie >10% contribution to the variance, Plate will be included as a factor in all analysis. Linear mixed effects models will be fitted by using the *limma* framework– for high dimensional omic data.

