Transcriptomic analysis: mRNA libraries will be sequenced on the Illumina HiSeq 4000 System targeting 30 million 150 bp paired-end reads, according to the manufacturer's protocol. The sequencing reads will undergo quality control using FastQC and will be mapped to GRCh38 using STAR v2.4.0g1 aligner. Transcript counts will be estimated using featureCounts. The transcriptome profiles will be filtered to remove low expression genes with cpm \leq 1 in at least 10% of samples using edgeR2. The transcriptome data will be normalized using voom in the limma R package and scaled from -1 to 1. Linear mixed effects models will be fitted for each blood transcript and cell fraction using the lme4 R package. Sex, age, challenge (peanut or placebo), time point (0, 2, 4 hours), reaction threshold (0-5), and interactions between time, challenge, and threshold will be included as fixed effects and a random intercept for each subject.

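### The SAP addendum's only transcriptomic model has no arm, visit or arm-by-visit term, so as written it gives no randomised comparison for primary mechanistic endpoint 7

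*SAP*

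**What the plan says.** The main SAP leaves this subject to its addendum: "This SAP covers study endpoints related to the primary and secondary clinical objectives and does not address the primary and secondary mechanistic objectives".

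The addendum's objective concerns mechanisms induced by daily sub-threshold ingestion, which is the randomised intervention. It then states: "We will test if peanut ingestion is associated with the following immune and transcriptomic processes". Change in transcriptional signatures is on the list that follows, and primary mechanistic endpoint 7 is "Change in peripheral blood transcriptional signature via RNAseq". Protocol 3.2.2 words endpoint 7 in nearly the same way. Protocol 13.2 words it differently, as data-driven identification of the pathways behind successful desensitization.

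The addendum has one transcriptomic model: "Linear mixed effects models will be fitted for each blood transcript and cell fraction using the lme4 R package". The fixed effects are "Sex, age, challenge (peanut or placebo), time point (0, 2, 4 hours), reaction threshold (0-5), and interactions between time, challenge, and threshold", with a random intercept for each subject.

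The same addendum treats its other assays as follows.
- ImmunoCAP: "The analysis will include a random subject effect and the fixed effect of randomization assignment, time, interaction between randomization assignment and time, and age".
- Cell frequencies: "Quantile-linear mixed effects models will be used for the frequency of %CD63+ basophil, peanut-specific Th2 cells and T cells", with no fixed effects listed.
- Epitope binding (BBEA): "Linear mixed effects models will be fitted by using the" limma framework, again with no fixed effects listed. Arm, visit and their interaction are named in that paragraph, but for the variance-component check of plate effects.

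**The concern.** A question about the effect of daily ingestion in a randomised trial needs a contrast between arms, and a question about change needs a contrast between visits. The transcriptomic model contains neither. Its time factor counts hours within a challenge day, and its challenge factor separates the peanut day from the placebo day. Neither says which diet the child was assigned to, or whether the sample came before or after the intervention period.

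An analyst who follows the addendum literally would report challenge effects by threshold and have no ingestion-versus-avoidance estimate for a primary mechanistic endpoint. An analyst who notices the gap would have to choose the arm contrast, the visits, the sampling time and the error control without a written rule. With one model per transcript, that leaves wide room for selective reporting.

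**Working it through.** No figure in the plan bears on this endpoint. The only power statement, about 85% with 36 per group, is for the primary clinical endpoint. The check is therefore mainly a comparison of texts, with a count of model terms.

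**1. What the hours mean.** Protocol 8.2 (baseline) and 8.3 (desensitization visit) take blood before the challenge starts and 2 and 4 hours after. The addendum's 0, 2 and 4 hours are these within-day draws, so the time factor does not stand for study visit.

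**2. Terms listed against terms needed.** Assume that each factor is coded categorically and the three-way interaction is included.
- Listed: sex (1) + age (1) + challenge × time × threshold cells (2 × 3 × 6 = 36, intercept absorbed) = 38 columns.
- Needed in addition: arm, visit, arm-by-visit = 3 columns, giving 38 + 3 = 41.
- A design-matrix check on a layout of 72 children with two challenge visits gave ranks of 38 and 41. The three missing contrasts are therefore not hidden combinations of the listed terms. Other coding of threshold changes the totals but not the three absent terms.

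**3. What follows.** Suppose threshold is the baseline value and age is age at enrolment. Each child then has the same covariate values at both DBPCFC visits for a given challenge and hour. With complete sampling, the fixed part predicts no change between visits in either arm, so its arm-by-visit difference is zero whatever the data show. The random intercept absorbs stable differences between children, and a true change between visits goes into the residual.

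**4. Search for a substitute.**
- Protocol 13.4.4 models clinical endpoints only.
- The main SAP excludes the mechanistic objectives.
- The limma sentence belongs to the BBEA paragraph and lists no terms; the transcript models use lme4.
- Protocol 13.2 gives endpoint 7 another wording but no model.

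**5. The seven primary mechanistic endpoints by stated terms.** Endpoints 1 and 2 (ImmunoCAP) state arm-by-time. Endpoints 3 to 6 name a model type without listing its fixed effects. Endpoint 7 alone has an explicit fixed-effect list that omits arm. The split is 2 + 4 + 1 = 7.

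**6. Error control.** SAP 6.1 sets a two-sided 0.05 level, and SAP 6.6 speaks only of secondary clinical endpoints. The documents give no transcript count. If 10,000 to 20,000 are assumed and none truly changes, an unadjusted 5% level flags 0.05 × 10,000 = 500 to 0.05 × 20,000 = 1,000 by chance. This supports stating a rule; the missing arm term does not depend on it.

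**The case against.** **Endpoint 7 says neither between arms nor from baseline, and Protocol 13.2 ties it to desensitization success.** This stands as a reading of the endpoint line alone. The randomised comparison is inferred from the objective above it, which asks what daily ingestion does. The Protocol 13.2 wording does not rescue the model, because no desensitization-outcome term is listed either. The two wordings do need to be reconciled.

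**Reaction threshold might carry the treatment effect.** The addendum does not say at which visit threshold is measured. If it were updated at follow-up, it could pick up some of the effect of the intervention. It would then be an outcome arising after randomisation, and its coefficient would not be a randomised contrast.

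**The model may be meant for another aim.** This is probably right. Six threshold levels, against four reaction-dose strata among randomised children (SAP 3.1.2), suggest that it was written for the wider screened cohort; that is an inference. It means the model should be kept and labelled, and that endpoint 7 still has none.

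A reader might infer more than the documents support:
- *That the addendum ignores arm throughout.* It does not. ImmunoCAP has an arm-by-time term, and endpoints 3 to 6 are under-specified rather than specified without arm.
- *That week-16 samples cannot be coded.* Neither arm has a DBPCFC at week 16, so a peanut-or-placebo factor would not fit. This matters only if RNA was collected then, and Protocol 9 does not list the visits for the RNA (Tempus) tubes.
- *That any later arm analysis is barred.* The SAP's purpose statement permits exploratory analyses and revision before data lock, and asks that unplanned analyses be identified as such. No lock date is given, and SAP 6.7 defines no separate mechanistic lock, so whether time remains cannot be judged.

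**Conclusion.** The concern holds in this form: the one stated transcriptomic model cannot answer the ingestion question posed for primary mechanistic endpoint 7, because arm, visit and arm-by-visit are missing and nothing elsewhere supplies them. The model remains suitable for describing the acute challenge response by threshold, which serves secondary mechanistic endpoint 2.

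The conclusion rests on reading the fixed-effect list as complete and peanut ingestion in the objective as the randomised diet. The text supports both. It does not rest on an assumed transcript count, effect size or correlation. The lack of a stated false-discovery rule is a related but secondary gap.

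This should be fixed, but its reach is limited to the mechanistic addendum. The primary clinical endpoint and its analysis are unaffected.

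**What to change.** In the addendum, for randomised children:

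1. Add a per-transcript mixed model with arm, visit, arm-by-visit, age, sex, baseline reaction-dose stratum and a subject random intercept. The visits are baseline and the desensitization DBPCFC, plus week 16 only if RNA was collected then.
2. Name the arm-by-visit contrast at the desensitization DBPCFC as the test of endpoint 7.
3. State which challenge day and time point supply the sample, since each DBPCFC runs over two days. The pre-challenge draw is a natural choice but not the only defensible one.
4. State a false-discovery rule across transcripts, for example Benjamini-Hochberg at 5%.
5. Reconcile the wording of endpoint 7 in Protocol 13.2 with Protocol 3.2.2 and the addendum. If the pathway wording is kept, say which model relates transcripts to desensitization outcome.
6. Keep the existing model, label it for the threshold and acute-reaction aim, and state that its threshold is the baseline value.

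The cost is one added model and addendum wording. No new visits are needed: Protocol 8.2, 8.3 and Table 2 already plan blood in both arms at baseline, week 16 and the desensitization DBPCFC. Before the text is settled, confirm at which of these visits Tempus tubes were drawn.

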### 3.1.1 Screening DBPCFC to determine threshold and identify subjects for randomization

Subject fulfilling inclusion/exclusion criteria will undergo an initial DBPCFC according to modified PRACTALL guidelines. Dosing is 3 mg, 10 mg, 30 mg, 100 mg, 300 mg, 600 mg, 1000 mg, 3000 mg, 4000 mg peanut protein. The dosing interval is 20-30 minutes except the final dose, 4000 mg, will be given 60 minutes after the 3000 mg dose. This baseline DBPCFC will phenotype participants as having LT peanut allergy, HT peanut allergy or no peanut allergy (Figure 1). Blood samples will be obtained in association with screening DBPCFC for mechanistic studies associated with peanut allergy endotypes. Those tolerating 9043 mg (approximately 8 teaspoons of peanut butter or equivalent) will be permitted to add peanut to the diet.

Figure 1. Initial screening DBPCFC to phenotype threshold, obtain biosamples, and identify those qualified for randomization.

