### 7.4 Rescue Medications

Treatment of individual allergic reactions should be with either an H1 and/or H2 antihistamine and/or epinephrine, along with IV fluids, albuterol and steroids as indicated. Subjects and parents will be trained in proper use of an epinephrine autoinjector and will be able to demonstrate proper technique.

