### AADCRC

The following procedures, assessments, and laboratory measures (windows for sample collection are detailed in the MOP as applicable) will be conducted, some of which to determine participant eligibility for the randomized trial:

- Physical exam, vital signs, complete medical history
- Spirometry (or peak flow under age 7 or if spirometry not allowed per COVID protocols)
- DBPCFC to peanut per modified PRACTALL (and associated examinations)
- Skin prick test to peanut
- Blood samples (before DBPCFC commences and 2 and 4 hours after starting; not to exceed 5cc/kg on a single day or 9.5ml/kg over any eight-week period per NIH guidelines). A saline lock may be placed to facilitate blood sampling at this and other visits where periodic samples are obtained.
- Quality of life survey, diet questionnaire, demographics
- Urine pregnancy if child bearing potential
- Saliva and stool collection

Screening takes place over 3 days (with one DBPCFC per day for 2 days). Each day is 4-8 hours.

If a participant reacts during the placebo arm of a DBPCFC, the DBPCFC may be repeated once. If a determination of reaction cannot be made due to unwillingness to repeat the DBPCFC or repeated placebo reactions, participation will end and any associated data will not be included in the analyses.

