# Desensitization DBPCFC visit, (week 72 or 8 weeks after reaching 1 Tablespoon or equivalent. Visit length 4-8 hours each of 2 days.

- Physical exam, vital signs, medical history
- Blood samples (before feeding challenge commences and 2 and 4 hours after starting; not to exceed 5cc/kg on a single day or 9.5ml/kg over any eight-week period per NIH guidelines)
- Spirometry or peak flow (optional under age 7)
- DBPCFC to peanut per modified PRACTALL (and associated examinations)
- Skin prick test to peanut
- Quality of life survey, diet questionnaire
- Urine pregnancy if child bearing potential
- Saliva and stool collection

This is the end of study visit for those not tolerating the DBPCFC and they will transfer to clinical management off of the study. Those tolerating the DBPCFC will proceed to the SU visit.

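### The post-challenge transcript and cell-fraction model takes no account of rescue treatment, so some peanut-response signals could be effects of the rescue drug

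*SAP*

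**What the plan says.** **Sampling.** At screening (Protocol 8.2) blood is taken "before DBPCFC commences and 2 and 4 hours after starting". At the desensitization visit (Protocol 8.3) it is taken "before feeding challenge commences and 2 and 4 hours after starting". The sustained-unresponsiveness visit has the same schedule. All these times count from the start of the challenge. Protocol 8.2 refers to the Manual of Procedures (MOP) for sample windows.

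**Dosing.** Protocol 3.1.1: "Dosing is 3 mg, 10 mg, 30 mg, 100 mg, 300 mg, 600 mg, 1000 mg, 3000 mg, 4000 mg peanut protein". On spacing: "The dosing interval is 20-30 minutes except the final dose, 4000 mg, will be given 60 minutes after the 3000 mg dose". Protocol 5.2 adds that dosing stops when symptoms are objective or persist, and leaves challenge details to the MOP.

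**Treatment of reactions.** Protocol 7.4 allows "H1 and/or H2 antihistamine and/or epinephrine, along with IV fluids, albuterol and steroids as indicated".

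**Analysis.** The SAP addendum, under Transcriptomic analysis, fits a linear mixed model to every transcript and cell fraction. The fixed effects are sex, age, challenge and the following: "time point (0, 2, 4 hours), reaction threshold (0-5), and interactions between time, challenge, and threshold will be included as fixed effects". A random intercept for each subject is added. Neither document gives a rescue term, a flag or exclusion for post-rescue samples, or a sensitivity analysis for rescue.

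**The concern.** Rescue is given because a child reacts, so it falls almost wholly on the peanut day. If a sample is drawn after epinephrine or a systemic steroid, the peanut-minus-placebo change from 0 hours contains the reaction and the drug together. A transcript or cell fraction that responds only to the drug could then be reported as responding to peanut.

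The existing terms do not separate the two. The placebo day seldom involves rescue, so it has nothing to subtract. Threshold is no substitute, because two children with the same threshold can be treated differently. Lower-threshold children also react earlier on the clock, so time since any rescue follows threshold, and a drug effect can enter the challenge-by-time-by-threshold terms as well.

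Change in the blood transcriptional signature is a primary mechanistic endpoint (Protocol 3.2.2), and biomarkers of the high-threshold phenotype are a secondary one (Protocol 3.3.2). The plan controls drug exposure before the challenge by restricting antihistamine and steroid use (Protocol 4.3). It does not address drugs given during the challenge.

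**Working it through.** The plan states no figure on this point, so there is none to reproduce. Two checks were made.

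**1. The dose clock.** Inputs are the ladder and intervals in Protocol 3.1.1. Time zero is the first dose, and no delays are assumed. The k-th dose, up to 3000 mg, is given at (k − 1) × 20 to (k − 1) × 30 minutes. The 4-hour draw is at 240 minutes.

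| Eliciting dose (cumulative) | Given at (min) | Minutes before the 4 h draw |
|---|---|---|
| 300 mg (443 mg), k = 5 | 80–120 | 120–160 |
| 600 mg (1043 mg), k = 6 | 100–150 | 90–140 |
| 1000 mg (2043 mg), k = 7 | 120–180 | 60–120 |
| 3000 mg (5043 mg), k = 8 | 140–210 | 30–100 |

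These are the four randomized strata (SAP 3.1.2). All of them receive the eliciting dose 30 to 160 minutes before the screening 4-hour draw. At the 2-hour draw (120 minutes), a child reacting at 300 mg has received that dose 0 to 40 minutes earlier. Low-threshold children, reacting at 100 mg (given at 60–90 minutes) or less, are past their eliciting dose by then. The exposure is therefore mainly at 4 hours for high-threshold children, and at both draws for low-threshold children.

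**2. Size of the effect.** None of these inputs comes from the documents: n = 72 peanut–placebo pairs, residual SD 1 per sample, an unadjusted two-sided 5% test, no true peanut effect, a share q treated before the sample, and a drug shift of d SD.

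- Contrast: (peanut 4 h − peanut 0 h) − (placebo 4 h − placebo 0 h).
- Expected value when only the drug acts: q × d.
- Standard error: four samples, each with variance 1, give √(4/72) = 0.236.
- False-flag probability: P(|Z + q·d/0.236| > 1.96).

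For example, q = 0.3 and d = 1 give 0.3/0.236 = 1.27. The probability is Φ(−0.69) + Φ(−3.23), about 25%.

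| Share treated | d = 1 SD | d = 0.5 SD |
|---|---|---|
| 10% | 7% | 6% |
| 30% | 25% | 10% |
| 50% | 56% | 19% |

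A simulation of the same contrast (4000 runs, 72 pairs, d = 1) gave 7% and 24% at 10% and 30% treated, and 5.7% with no drug effect. The result depends on n. At d = 1 and 30% treated, the simulation gave about 16% with 36 pairs and 42% with 150. The number of pairs is uncertain because low-threshold and tolerant children also contribute mechanistic samples (Protocol 8.2).

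**The case against.** **Post-rescue sampling is inferred.** No passage says that blood was drawn after rescue. It follows from the fixed draw times, the dose clock and the treatment rule. The MOP, which is not among the documents, may time or withhold draws after treatment. This stands: a reader might infer that such samples certainly exist, but the text supports only that they can. The SAP model refers to no such rule.

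**Treatment may be antihistamine alone.** Protocol 7.4 permits that, and the documents do not say how often epinephrine or steroids are given at challenge. This stands too, and it is why the size can only be shown as a range.

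**The arms may not differ.** A reader might infer from the planning success rates (46% against 12.25%) that controls react more at the desensitization challenge, receive more rescue, and so bias an arm or responder comparison. The documents do not support this. Success means tolerating at least two steps more or the full 9043 mg, so a success can still react. Failure does mean reacting, so the planning rates put reactions at 87.75% to 100% in controls (100 − 12.25) and 54% to 100% in consumers (100 − 46). These ranges overlap. The model also has no arm or responder term.

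**A larger effect can be computed.** With a standard error of √(2/72), the 1 SD figures become 9%, 44% and 85%. That error fits a single-time peanut–placebo difference with SD 1. It does not fit the baseline-adjusted contrast under a residual SD of 1.

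**Excluding post-rescue samples brings its own bias.** Rescue follows severity, so exclusion conditions on something that happens after the challenge and removes the stronger reactors. This stands and shapes the fix.

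**Conclusion.** The point holds as a cheap improvement to a mechanistic analysis. The model makes no provision for rescue, the schedule allows post-rescue samples on the peanut day, and neither the placebo day nor the threshold terms can remove a drug effect. Drug-responsive transcripts or cell fractions could be read as peanut-response signals.

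The actual size is unknown. Under the stated assumptions, the chance of a false flag stays close to the nominal 5% when 10% of children are treated. With half treated, it reaches about 19% at a 0.5 SD shift and 56% at 1 SD. The addendum names no gene-level significance threshold, so the 5% test is itself an assumption.

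The reach is limited to the 2-hour and 4-hour post-challenge samples. The primary and secondary clinical endpoints, pre-challenge samples and week 16 samples are not affected.

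**What to change.** In the SAP addendum, under Transcriptomic analysis:

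1. Flag each 2-hour and 4-hour sample as taken before or after the first rescue epinephrine or systemic steroid dose, using the challenge treatment record. If the MOP already has a rule for such samples, cite it.
2. Keep the all-sample model as planned, and describe its contrast as the peanut reaction plus any treatment of it.
3. Add a sensitivity fit that excludes post-rescue samples. Report effect sizes and direction from both fits side by side, and mark genes and cell fractions whose estimate changes materially, with the criterion set in advance.
4. Do not require significance in both fits. The restricted set is smaller and milder, so that rule would discard genuine reaction genes.

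Sampling and rescue rules stay as they are.

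The cost is a few sentences, one derived variable and one extra model run. The restricted fit has fewer 4-hour samples and leans toward milder reactors, so attenuation alone does not prove a drug artefact. It should be read beside the planned fit, not in place of it.
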